### 6.3.7 Sensitivity Analysis

Sensitivity analysis will be carried out for possible intercurrent events such as discontinuation due to AE, lack of efficacy and use of rescue and prohibited medication. New estimands associated to each intercurrent event will be added to the already existing primary estimand accordingly.

### 6.3.8 Exposure to Treatment

Subjects will record each IMP or placebo administration (e.g., one drop every six hours, during 14 days) on their dispensed diaries.

Compliance is defined as the percentage of actual doses the patient instilled with respect to the number of total doses planned. The planned dose is always one drop of IMP or placebo. Compliance will be summarized categorically (<80%, ≥80% and 100%) by treatment regime. It will be calculated as follows:

Compliance of IMP/Placebo administered % = (num. of doses instilled / num. of planned doses) )(ml))\*100

Planned doses=56

Compliance at last visit with IMP/Placebo is defined as the percentage of actual doses the patient instilled with respect to the number of total doses planned at the time of the last visit with IMP/Placebo.

Compliance of IMP/Placebo administered % at last visit with IMP/Placebo = (num. of doses instilled / num. of planned doses at last visit with IMP/Placebo))(ml)\*100

Planned doses at last visit with IMP/Placebo = (End date IMP/Placebo exposure – First date IMP/Placebo exposure)\*4.

Compliance at visit 3 (day 8±1) is defined as the percentage of actual doses the patient instilled with respect to the number of total doses planned at visit 3.

Compliance of IMP/Placebo administered % at visit 3= (num. of doses instilled / num. of planned doses at visit 3 )(ml)\*100

Planned doses at visit 3=32

In case a scheduled dose was not administered (missed) the missed dose and the reason will be captured in the eCRF as per the patient diary and tabulated by treatment regimen.

All compliance data will be summarized and listed for the SAF.

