The investigator will administer the first dose of IMP on Day 1 at the study center. Study medication will be then dispensed to patients for self-administration during the study at a dosage of one drop QID during 14 days.

Patients will be provided with diaries to record their daily dosing. Doses should be administered approximately 6 hours apart. In addition, patients will be asked to make note of any missed doses and the reason for the missed dosage. The intent is to capture missed doses, *per se*, rather than a shifted dosing schedule.

As this is a double-masked study, all patients, investigators, sub-investigators, and center personnel involved in measuring, monitoring and obtaining data in the study will be masked to patient treatment assignment. The study medication will be packaged in a masked fashion and will be administered and dispensed by the investigator according to patients' randomization numbers. In addition, all Sponsor's and vendors' personnel involved in the on-site monitoring and direct management of the data and study centers will remain masked to individual patient data.

Protocol waivers of exemptions are not allowed with the exception of immediate safety concerns. Therefore, adherence to the study design requirements, including those specified in the Table 1, are essential and required for study conduct.

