## 4 OVERALL STUDY DESIGN

## 4.1 Overview of Study Design

This is a Phase 3, randomised, parallel-group, placebo-controlled, double-masked, multicentre study to assess the efficacy and safety of clobetasol propionate ophthalmic nanoemulsion 0.05% in the treatment of inflammation and pain associated with cataract surgery.

All randomized patients will undergo routine cataract surgery according to the investigator's normal procedures being surgery day considered Day -1 of the study, whereas the day of the randomization/first administration will be considered study Day 1. First administration of the Investigational Medicinal Product (IMP) will take place at the study center, whereas the rest of study medication will be dispensed to patients for self-administration at a dosage of one drop every six hours, four times a day (QID) during 14 days as well as a diary to record the drug instillations.

Figure 1. Diagram of Study Design

\* Patients who, for any reason, withdraw from the study treatment will be highly encouraged to continue attending all their remaining study visits to collect the most complete efficacy and safety data.

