#### 5 DATA SETS TO BE ANALYSED

The following analysis sets will be used for the statistical analysis and presentation of data:

- **Full Analysis Set (FAS):** The FAS will be the primary analysis set for the efficacy endpoints and will include all randomized patients. The FAS population will be analyzed according to the planned treatment (rather than treatment actually received).

- **Safety Analysis (SAF) set** The safety set will be the primary analysis set for the safety endpoints and will include all randomized patients who instilled at least one dose of IMP or placebo. The SAF will be analyzed according to the treatment actually received.
- **Per Protocol (PP) Population:** The PP population set will be tested to confirm the robustness of the efficacy analyses and will include all patients in the FAS who have no major protocol deviations (i.e. patients who comply the protocol sufficiently to ensure that the data exhibits the effects of the IMP or placebo when administered as intended). Protocol violations include: violations of entry criteria, lack of compliance and the use of prohibited medication. The PP population will be analyzed according to the treatment actually received.

Lack of compliance is defined as less than 80% compliance (section 6.3.8).

Efficacy analyses will be based on both the FAS and the PP, but the FAS will be considered the primary analysis population.

Safety analyses will be based on the SAF.

For the efficacy endpoints only visits with IMP and without prohibited/rescue medication will be analyzed for FAS population.

For the efficacy endpoints based in PP population (primary efficacy analysis and key secondary at visit 3) will include all patients in the FAS population who have no major protocol deviations. Without violations of eligibility criteria, lack of compliance at visit 3 (see section 6.3.8 for details) and without the use of rescue/prohibited medication until visit 3.

Only study eye will be analyzed and presented in tables and the non-study eye will only be included in listings.

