## 6.3 Hypotheses and Statistical Methods

### 6.3.1 Definitions

Baseline	( Visit 1 (Day 1, 24 h after the cataract surgery).
Time calculation	Differences between dates to express duration will be calculated as the final date - initial date + 1. To convert these days differences to other units, the following conversion factors will be used: 1 year = 365.25 days and 1 month = 30.4375 days.  Ex. Age = (informed consent date – date of birth + 1) / 365.25
Absolute change from Baseline	Absolute change from Baseline at Visit X will be calculated as:  Absolute change from Baseline = Visit X - Baseline
Percentage change from Baseline	Percentage change from Baseline at Visit X will be calculated as:  Percentage change from Baseline [%] = ((Visit X - Baseline)/Baseline) *100  In case of Baseline = 0 no percentage change from baseline will be calculated.
Signs of ocular inflammation (yes/no)	The presence/absence of the different signs of ocular inflammation: Chemosis, Bulbar conjunctival injection, ciliary injection, corneal edema, keratic precipitates will be defined as:  No: grade=0 (absence)  Yes: grade=1, 2 or 3 (presence)
Conversion Snellen to LogMar	Step 1. Mar = Snellen Denominator/Snellen Numerator  Step 2. LogMar = log (Mar)  Example: Snellen 20/40  Mar = 40/20 = 2  LogMar= log(2) = 0.3
Treatment Emergent Adverse Event	Treatment Emergent Adverse Events (TEAEs) are defined as an event that emerges during treatment  having been absent pre-treatment or worsens relative to the pre-treatment state:  First dose IMP/Pacebo date ≤ start date AE ≤ last dose IMP/Placebo date
Rescue medication	The following prohibited medications will be considered as rescue medication when administered to subjects not responding to IMP or placebo: 

▪ Any systemic or local therapy with corticosteroids (other than the study drug) or immunosuppressant (except pre-surgical and/or surgical administration of 1 drop of a topical NSAID or corticosteroid, at the investigator discretion)

▪ Any topical ocular medication (except preservative-free antibiotics for prophylactic purposes and preservative-free artificial tears)

	

▪ Any systemic NSAID or opioids drugs (except occasional use of OTC formulations titrated no more than one single dose per week)

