Relative day	
The relative day of an event that occurs prior to administration of IMP:
 

• Relative day = (Start date)-(Date of administration of IMP).

 
The relative day of an event that occurs on the same day or after administration of IMP:
 

• Relative day = (Start date)-(Date of administration of IMP)+1.

 
Consequently, Day 1 is the same day as the day of administration of IMP, Day -1 is the day before, and Day 2 is the day after.

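### The last-visit planned-dose formula in SAP 6.3.8 does not count doses as the rest of the SAP does: it can be four too low or two too high, and it is zero for a Day 1 stop

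*SAP*

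**What the plan says.** SAP 6.3.8 defines three compliance percentages, each the doses instilled divided by the doses planned.

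- Whole course: "Planned doses=56".
- Visit 3: "Planned doses at visit 3=32".
- Last visit on treatment: "Planned doses at last visit with IMP/Placebo = (End date IMP/Placebo exposure – First date IMP/Placebo exposure)\*4".

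The general date rule in SAP 6.3.1 is: "Differences between dates to express duration will be calculated as the final date - initial date + 1". The same section numbers the day of first administration as Day 1. The regimen in SAP 4.1 is "one drop every six hours, four times a day (QID) during 14 days". Protocol 4.1 adds: "The investigator will administer the first dose of IMP on Day 1 at the study center". Day 1 may therefore be a partial dosing day.

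SAP 5 sets the cut-off: "Lack of compliance is defined as less than 80% compliance (section 6.3.8"). For the per-protocol analyses of the primary and key secondary endpoints it specifies compliance at Visit 3. For the general per-protocol set it does not say which of the three percentages applies.

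**The concern.** The last-visit formula subtracts two dates without adding one, so it counts one calendar day fewer than the inclusive rule. Two measures in the same section can then classify the same patient differently from the same dates and doses. The last-visit measure is the only one of the three whose denominator changes with the date treatment ended. An error in it therefore shows most in patients who stopped early, where one day is a large share of the exposure. At stake are the reported compliance of those patients and, if this measure decides who is compliant, their place in the general per-protocol set.

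**Working it through.** **Inputs.** Four doses a day for 14 days (SAP 4.1); first dosing day is Day 1 (SAP 6.3.1); planned doses of 56 and 32 and the last-visit formula (SAP 6.3.8); cut-off of 80% (SAP 5).

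**Step 1: reproduce the plan's own figures.** Counting both end days, planned doses for a last dose on Day d are 4d.

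- Day 1 to Day 14: 4 × 14 = 56, as stated.
- Day 1 to Day 8: 4 × 8 = 32, as stated.

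**Step 2: apply the last-visit formula to the same dates.** It gives 4(d − 1).

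- Day 14: 4 × 13 = 52.
- Day 8: 4 × 7 = 28.

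**Step 3: size of the error when the first and last days are both full.** The shortfall is 4d − 4(d − 1) = 4 doses, and the overstatement factor is d/(d − 1). The fewest doses that read as 80% or more is 0.8 × 4(d − 1), rounded up to a whole dose. True adherence is that number over 4d.

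| Last dosing day | Inclusive count | Formula | Full dosing reads as | Fewest doses reading ≥80% | True adherence at that point |
|---|---|---|---|---|---|
| 2 | 8 | 4 | 200.0% | 4 | 50.0% |
| 3 | 12 | 8 | 150.0% | 7 | 58.3% |
| 5 | 20 | 16 | 125.0% | 13 | 65.0% |
| 8 | 32 | 28 | 114.3% | 23 | 71.9% |
| 14 | 56 | 52 | 107.7% | 42 | 75.0% |

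Two examples:

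- A patient has a last dose on Day 8 and 25 doses instilled. Visit 3 compliance is 25/32 = 78.1%, below the cut-off. Last-visit compliance is 25/28 = 89.3%, above it.
- At Day 14, 80% of 56 is 44.8, so 45 doses should be needed. With 42 to 44 doses the patient is at 75.0% to 78.6% on 56, but 80.8% to 84.6% on 52.

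**Step 4: partial first and last days.** Assume k1 doses are possible on the first day and k2 on the last, each from 1 to 4, with the last day later than the first. Planned doses are k1 + k2 + 4(d − 2). Subtracting 4(d − 1) leaves k1 + k2 − 4.

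- Largest shortfall: 4 + 4 − 4 = 4 doses too few.
- Largest excess: 1 + 1 − 4 = −2, so two doses too many.
- No error when k1 + k2 = 4.

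Illustrations at 6-hour spacing:

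- First drop 10:00 on Day 1, last 22:00 on Day 14 (k1 = 3, k2 = 4): 55 scheduled, formula 52.
- First drop 14:00, last 02:00 on a later date (k1 = 2, k2 = 1): the formula is one dose too large.

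**Step 5: a stop on Day 1.** The formula gives 4 × (1 − 1) = 0, so compliance is undefined. SAP 6.3.8 has no rule for this, and no cap at 100%.

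**The case against.** The best defence is that the formula measures elapsed time and suits strict 6-hourly dosing. The 56th dose falls 55 × 6 = 330 hours, or 13 days 18 hours, after the first. If the first drop is given at the centre at 06:00 or later, a fully adherent completer finishes on Day 15, and the formula gives 4 × (15 − 1) = 56, which is correct. The figure of 56 alone therefore does not prove inclusive counting. The rule in SAP 6.3.1 is also about durations, so extending it to a dose count is an interpretation.

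All of that stands. It does not rescue the formula, which is right only when k1 + k2 = 4, a condition the SAP nowhere states. Nor can it return the SAP's own 32 for a nominal Day 8.

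A reader might infer three stronger things that the documents do not support.

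- **That the formula always understates planned doses.** It does not: Step 4 shows it can be exact, or up to two doses too large.
- **That the per-protocol check on the primary or key secondary result is compromised.** SAP 5 ties those analyses to Visit 3 compliance, with the fixed 32, and the only per-protocol efficacy tables listed in SAP 8.1 are at Visit 3. SAP 6.3.6.2 does mention per-protocol testing of the other secondary endpoints, but they are exploratory and no such tables are listed.
- **That early stoppers are necessarily kept in the general per-protocol set.** Nothing ties the last-visit measure to the 80% cut-off. If the whole-course measure were used, a Day 8 stopper could reach at most 32/56 = 57.1% and would already fail.

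**Conclusion.** The concern holds in a limited form. The last-visit formula is inconsistent with the inclusive date rule and with the Visit 3 denominator beside it. The d/(d − 1) overstatement and the adherence figures in the table assume that the first and last days are both full dosing days; with partial days the discrepancy can shrink, vanish or reverse. The zero denominator for a Day 1 stop needs no such assumption.

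The consequence is wrong or undefined last-visit percentages in the compliance summary (Table 14.3.5.1) and listing (Listing 16.2.5). An effect on the general per-protocol set is possible only if this measure is the one compared with 80%. The FAS primary test, the Visit 3 per-protocol analyses, the sample size and the significance level are not affected. It should be corrected because the error is plain and the remedy is cheap.

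**What to change.** In SAP 6.3.8, define last-visit planned doses as the number of doses scheduled from the first to the last dosing time, counting both ends and capped at the plan's own 56. An equivalent form is (End date − First date + 1) × 4, less the doses not possible on partial first and last days. Either gives a Day 1 stop at least one planned dose, which removes the zero denominator.

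Adding 1 and nothing else would not be enough. The 6-hourly completer ending on Day 15 would be assigned 60 doses and read 56/60 = 93.3%. A patient dosed on schedule from 10:00 on Day 1 to 04:00 on Day 3 takes all 8 scheduled doses, but would be assigned 12 and read 66.7%.

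In SAP 5, state which of the three compliance measures is held against 80% for patients who stop treatment early.

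The cost is a few lines in the SAP before unmasking. Some patients will show lower compliance than under the present formula.

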### 6.3.9 Concomitant Medications

All concomitant medications/therapies will be classified according to ATC level 3 group text and generic medication name. The medications will be divided into two categories based on start date and end date: Prior Medications and Concomitant Medications: .

- Prior Medications: start date and end date before first day of IMP
- Concomitant Medications:
  - Start date before first day of IMP and end date after or on same day as first day of IMP or no end date, i.e. ongoing after first day of IMP; or |
  - Start date after or on same day as first day of IMP

Within concomitant medications, a distinction will be made between rescue medication and prohibited medication.

Incomplete dates will be handled as follows:

- If the start and stop date for a concomitant medication are completely missing, it will be assumed that the medication was started before treatment and classified as Prior Medication.
- If only the start date is missing the medication will be classified as:
  - Prior if end date is before first day of IMP
  - Concomitant if end date is on or after first day of IMP
- If only the end date is missing the medication will be classified as
  - Concomitant if start date is before or on same day as Day 15
- If the year and/or month are available, medication start in relation to the first day of IMP will be evaluated as close as possible (e.g., if only the year when the medication was started is available and ongoing is checked, the medication will be classified as a Concomitant Medication).

- If the medication was started in the same month as the first day of IMP, the medication will be classified as a Concomitant Medication.

Relative day will generally be calculated for all medications except for the ones with an incomplete start date.

Data will be listed for the SAF. Subject's medications will be presented separately for each timing (i.e. prior, and concomitant medications) in 2 summary tables. In addition, a summary table for rescue and prohibited medication will be presented distinguishing each one in a column.

In the listings will show whether the concomitant medication is rescue medication or prohibited medication.

Rescue medication shall be as reported as such in the eCRD. The following ATC3 codes of concomitant medication will be considered as prohibited medication if they are not classified as rescue medication (all medications will be reviewed and it will be considered whether any medication should be included or excluded in the prohibited classification):

- D07A - Corticosteroids, plain
- D07B - Corticosteroids, combinations with antiseptics
- D07C - Corticosteroids, combinations with antibiotics
- D07X - Corticosteroids, other combinations
- G01B - Combinations of corticosteroids and antiinfectives for gynaecological use
- A01AC - Corticosteroids for local oral treatment
- D01A - Corticosteroids in combination with antifungals
- D10AA - Corticosteroids, combinations for treatment of acne
- C05AA - Antihemorrhoidals with corticosteroids
- S01B – Antiinflammatory agents
- S02B - Corticosteroids
- S02C - Corticosteroids and antiinfectives in combination
- S03B - Corticosteroids
- S03C - Corticosteroids and antiinfectives in combination.
- H02 - Corticosteroids for systemic use.
- L04A - Immunosuppressants
- M01A - Antiinflammatory and antirheumatic product, non-steroids
- N02BE - NSAIDs in combination with paracetamol.
- M01B - Salicylates in combination with corticosteroids.
- M01B - Combinations of antiinflammatory/antirheumatic agents
- N02A - Opioids
- Any ATC3 with ocular route except for S01A, S03A (Antiinfectives) preservative-free for prophylactic purposes and S01X (Other ophthalmologicals) preservative-free.

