#### **7.5.3 *Prior and Concomitant Medication***

Prior medications taken within 2 months prior to the Screening visit (Visit -1) (36 months prior for ocular implants and/or intravitreal injections) will be recorded at the Screening Visit (Visit -1), including OTC products.

Concomitant medications (including OTC products) and its duration will be recorded in the concomitant medication log/section of the eCRF throughout the study.

Prior medication is defined as medication received prior to first IMP intake. Any medication received at least once after the first IMP intake will be considered as concomitant medication. This means, a medication might be assigned to both, prior and concomitant medication. If no unambiguous assignment to prior and concomitant medication is possible due to incomplete or missing dates, the medication will be assigned to both, prior and concomitant medication.

---

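### SAP 6.3.9 classes medication with no dates as Prior only, contrary to Protocol 7.5.3, so undated prohibited use can escape the FAS visit exclusion and the PP exclusion

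*SAP*

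**What the plan says.** Protocol 7.5.3 lets a medication belong to both categories, and for unclear timing it rules: "If no unambiguous assignment to prior and concomitant medication is possible due to incomplete or missing dates, the medication will be assigned to both".

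SAP 6.3.9 splits medications into two categories. Prior needs a start and an end before the first day of IMP. A medication started before that day with no end date, meaning ongoing, is Concomitant. For a record with neither date the rule is: "If the start and stop date for a concomitant medication are completely missing, it will be assumed that the medication was started before treatment". The class given is Prior.

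The same section ties two further classifications to the concomitant category:

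- "Within concomitant medications, a distinction will be made between rescue medication and prohibited medication".
- "The following ATC3 codes of concomitant medication will be considered as prohibited medication if they are not classified as rescue medication".

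Rescue is identified by report: "Rescue medication shall be as reported as such in the eCRD" (evidently the eCRF). On the prohibited list, the SAP adds in parentheses that "all medications will be reviewed and it will be considered whether any medication should be included or excluded in the prohibited classification".

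SAP section 5 uses these labels. FAS efficacy analyses take only visits on IMP and free of prohibited or rescue medication. The PP analyses at Visit 3 exclude patients who used either up to that visit.

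**The concern.** The SAP states that it is based on the amended protocol, yet it replaces a cautious rule (unclear timing counts in both categories) with a permissive one (Prior only) and gives no reason. Protocol 9.2 asks for departures from the planned analysis to be described and justified.

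The label is more than a matter of tabulation, because the prohibited screen runs only on medication already classed as concomitant. A wholly undated topical steroid or NSAID, not reported as rescue, would be classed as Prior and never compared with the list. The patient's Visit 3 would be analysed when section 5 says it should not be, and the patient would stay in a PP set meant to be free of such use. A Day 8 cell grade of 0 that may owe something to another anti-inflammatory would then count as a response.

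**Working it through.** **Step 1. The two rules side by side, both dates missing.**

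| Source | Class | Screened against the prohibited list? |
|---|---|---|
| Protocol 7.5.3 | Prior and concomitant | Yes, through the concomitant class |
| SAP 6.3.9 | Prior only | No, read literally |

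**Step 2. The SAP rule against the SAP's own definitions.** The rule assumes only that the drug was started before treatment; nothing is assumed about when it stopped. Prior requires an end before the first dose, which is not known. A start before IMP with no end date is Concomitant by definition. The rule for a missing end date alone also gives Concomitant when the start is on or before Day 15. Same-month starts, and year-only starts marked ongoing, go to Concomitant too. The record with the least information therefore gets the least cautious class.

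**Step 3. What depends on the label.**

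- Prohibited use: found by drug class within concomitant medication, then used in SAP section 5 for FAS visits and PP membership. It is exposed to the date rule.
- Rescue: taken from the eCRF report, so it should not depend on dates. The doubt is that the SAP draws the rescue/prohibited distinction within concomitant medication, and an undated rescue record would be classed as Prior.
- Timing: even a correctly labelled undated record cannot be placed before or after Visit 3, since SAP 6.6 imputes nothing when no date field is available.

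**Step 4. Size.** The documents give no rate of undated records, so only the effect per patient can be shown. The planning inputs (Protocol 9.1.1) are 0.22 against 0.07, 2:1, N = 202. They reproduce: the pooled proportion is (2 × 0.22 + 0.07)/3 = 0.17, and the two-sided 0.05 chi-square test without continuity correction has power 0.80. At 140 and 70 these rates give about 31 (0.22 × 140 = 30.8) and 5 (0.07 × 70 = 4.9) responders. Take 31 and 5 as the counts when the affected patient is handled correctly.

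The SAP does not say whether a Visit 3 removed under section 5 counts as failure or leaves the denominator. One patient wrongly kept in changes the rate as follows:

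| Correct handling | Day 8 grade | Active | Placebo |
|---|---|---|---|
| Counts as failure | 0 | 32/140 − 31/140 = +0.7 points | 6/70 − 5/70 = +1.4 points |
| Leaves denominator | 0 | 32/140 − 31/139 = +0.6 points | 6/70 − 5/69 = +1.3 points |
| Leaves denominator | above 0 | 31/140 − 31/139 = −0.2 points | 5/70 − 5/69 = −0.1 points |

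On the first row's reading, the chi-square p-value starts at 0.0066 (31/140 against 5/70) and moves thus:

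| Patients wrongly counted as responders | All on placebo | All on active |
|---|---|---|
| 1 | 0.015 | 0.0048 |
| 2 | 0.031 | 0.0036 |
| 3 | 0.060 | 0.0026 |

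These counts are assumed for illustration; they are not a forecast.

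**The case against.** A reader might infer that undated rescue or prohibited use drops out of the failure definition. The documents do not support that. Failure and non-response are tied to rescue alone (Protocol 6.7.2 and 9.1.10, SAP 6.3.5), so prohibited use that is not rescue was never in the definition. Rescue is identified by report. A rescued patient also stops the IMP (Protocol 6.7.2), and SAP section 5 admits only visits on IMP, so the exposure end date is a second marker. This objection stands. For rescue, only an ambiguity in wording remains.

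There are also safeguards. Protocol 6.7 requires start and stop dates for every medication, and Protocol 10.6 provides for validation and queries. Prohibited medication is a major deviation (Protocol 10.4), and a masked review assigns patients to analysis sets (Protocol 9.1.7, SAP 6.2). SAP 6.3.9 has medications reviewed for the prohibited classification. These points make the case rare and may catch some instances. They do not remove the defect: none expressly covers items already classed as Prior, and the medication review is mentioned in the sentence about concomitant medication.

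Finally, Protocol 7.5.3 sits under baseline characteristics and says nothing about rescue or PP membership. Medication history reaches back 2 months, or 36 months for ocular implants and intravitreal injections, and a single peri-surgical drop of a topical NSAID or corticosteroid is permitted. Assigning every undated item to both categories could flag historical or permitted use. That is fair, and the fix has to allow for it.

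**Conclusion.** The contradiction is real: SAP 6.3.9 departs from Protocol 7.5.3 without explanation and does not fit its own definition of Prior. Read literally, it lets undated prohibited use bypass both exclusions in SAP section 5. Reported rescue probably survives, but the SAP should say so.

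The point is minor. It needs both dates to be missing on a drug of a prohibited class, used after treatment began, not reported as rescue and not caught in review. Per patient the shift is at most 0.7 points on active or 1.4 on placebo, smaller if excluded visits leave the denominator. Nothing in the documents shows a net bias toward the active arm: a wrongly counted placebo responder weakens the apparent effect and an active one strengthens it. The illustration shows that two or three such patients in the smaller arm could matter, which is reason enough to settle the rule before unmasking.

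**What to change.** In SAP 6.3.9:

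1. Replace the rule for records with both dates missing by that of Protocol 7.5.3: assign to both categories, and screen for prohibited status in the masked review. Do not flag use documented as pre-treatment, or the permitted peri-surgical drop.
2. State that a medication reported as rescue in the eCRF counts as rescue whatever its date class.
3. State how undated rescue or prohibited use is placed relative to Visit 3, for example as before Visit 3 unless other records, such as the exposure end date, show otherwise.

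The cost is a few sentences, with no new data collection and no change to sample size. A few historical medications may need manual review or may be flagged conservatively.
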